## 8. SAFETY MONITORING AND REPORTING

### 8.1. Adverse Events

#### 8.1.1. Definitions

For the purposes of this Protocol, an adverse event (AE) is defined as any untoward medical occurrence associated with the use of a drug in humans, whether or not considered drug related, that occurs after a subject provides informed consent. Abnormal laboratory values or test results occurring after informed consent constitute AEs only if they induce clinical signs or symptoms, are considered clinically meaningful, require therapy (eg, hematologic abnormality that requires transfusion), or require changes in the study drug(s).

#### 8.1.2. Reporting

Adverse events that begin or worsen after informed consent should be recorded on the Adverse Events form of the eCRF. Conditions that were already present at the time of informed consent should be recorded on the Medical History form in the eCRF. Monitoring for the occurrence of new AEs should be continued for at least 30 days after the last dose of study drug. Adverse events (including laboratory abnormalities that constitute AEs) should be described using a diagnosis whenever possible rather than by individual underlying signs and symptoms. When a clear diagnosis cannot be identified, each sign or symptom should be reported as a separate AE.

The term "disease progression" should be recorded as an AE/SAE only if there are no other identifiable AEs/SAEs associated with the disease progression at the time of reporting. For events associated with disease progression, the relevant signs and symptoms should be reported using a diagnosis whenever possible rather than individual underlying signs and symptoms. When a clear diagnosis cannot be identified, each sign or symptom should be reported as a separate AE. If the events resulting from disease progression meet the criteria for an SAE (eg, resulted in hospitalization, a life-threatening event, or death), the specific event(s) should be reported as an SAE(s) as described in Section 8.3.2. In both cases (ie, AEs or SAEs related to disease progression), it should be indicated that each event (reported as a diagnosis or as signs and symptoms) is related to disease progression on the Adverse Events form of the eCRF.

The severity of AEs will be assessed using CTCAE v4.03 Grades 1 through 5. If an event is not classified by CTCAE, the severity of the AE will be graded according to the scale below to estimate the grade of severity:

Grade 1	Mild; asymptomatic or mild symptoms; clinical or diagnostic observations only; intervention not indicated.
Grade 2	Moderate; minimal, local, or noninvasive intervention indicated; limiting age-appropriate activities of daily living.
Grade 3	Severe or medically significant but not immediately life-threatening; hospitalization or prolongation of hospitalization indicated; disabling; limiting self-care activities of daily living.
Grade 4	Life-threatening consequences; urgent intervention indicated.
Grade 5	Death due to AE

The occurrence of AEs should be sought by nondirective questioning of the subject during the screening process after signing the ICF and at each visit during the study. Adverse events may also be detected when they are volunteered by the subject during the screening process or between visits, or through physical examination, laboratory test, or other assessments. To the extent possible, each AE should be evaluated to determine:

- The severity grade (CTCAE Grade 1 to 4).
- Whether there is at least a reasonable possibility that the AE is related to the study treatment: suspected (yes) or not suspected (no).
- The start and end dates, unless unresolved at final follow-up.
- The action taken with regard to study drug.
- The event outcome (eg, not recovered/not resolved, recovered/resolved, recovering/resolving, recovered/resolved with sequelae, fatal, unknown).
- The seriousness, as per serious adverse event (SAE) definition provided in Section 8.3.1.

Unlike routine safety assessments, SAEs are monitored continuously and have special reporting requirements (see Section 8.3.2).

All AEs should be treated appropriately. If an AE is treated with a concomitant medication or nondrug therapy, this action should be recorded on Adverse Event form and the treatment should be specified on the Prior/Concomitant Medications or Procedures and Non-Drug Therapy form in the eCRF.

Once an AE is detected, it should be followed until it has resolved or until it is judged to be permanent; assessment should be made at each visit (or more frequently if necessary) of any changes in severity, the suspected relationship to the study drug, the interventions required to treat the event, and the outcome.

When the severity of an AE changes over time for a reporting period (eg, between visits), each change in severity will be reported as a separate AE until the event resolves. For example, 2 separate AEs will be reported if a subject has Grade 1 diarrhea, meeting the definition of an AE, that lasts for 3 days before worsening to a Grade 3 severity. The Grade 1 event will be reported as an AE with a start date equal to the day the event met the Grade 1 AE definition and a stop date equal to the day that the event increased in severity from Grade 1 to Grade 3. The Grade 3 event will also be reported as an AE, with the start date equal to the day the event changed in intensity from Grade 1 to Grade 3 and a stop date equal to the day that the event either changed severity again or resolved.

## **8.2. Laboratory Test Abnormalities**

Laboratory abnormalities that constitute an AE in their own right (considered clinically meaningful, induce clinical signs or symptoms, require concomitant therapy, or require changes in study drug) should be recorded on the Adverse Event form in the eCRF. Whenever possible, a diagnosis rather than a symptom should be provided (eg, "anemia" instead of "low hemoglobin"). Laboratory abnormalities that meet the criteria for AEs should be followed until they have returned to normal or an adequate explanation of the abnormality is found. When an abnormal

laboratory test result corresponds to a sign or symptom of a previously reported AE, it is not necessary to separately record the laboratory test result as an additional event.

Laboratory abnormalities that do not meet the definition of an AE should not be reported as AEs. A Grade 3 or 4 AE does not automatically indicate an SAE unless it meets the definition of serious, as defined in Section 8.3.1. A dose modification for the laboratory abnormality may be required (see Section 5.4) and should not contribute to the designation of a laboratory test abnormality as an SAE.

### **8.3. Serious Adverse Events**

#### **8.3.1. Definitions**

An SAE is defined as an event that meets at least 1 of the following criteria:

- Is fatal or life-threatening.
- Requires inpatient hospitalization or prolongation of existing hospitalization, unless hospitalization is a result of:
  - A routine treatment or monitoring of the studied indication not associated with any deterioration in condition.
  - An elective surgery or preplanned treatment for a pre-existing condition that is unrelated to the indication under study and has not worsened since signing the ICF.
  - A treatment on an emergency outpatient basis for an event not fulfilling any of the definitions of a SAE and not resulting in hospital admission.
  - Any social reasons and respite care, in the absence of any deterioration in the subject's general condition.
- Results in persistent or significant disability, incapacity, or a substantial disruption of a person's ability to conduct normal life functions.
- Constitutes a congenital anomaly or birth defect.
- Is considered to be an important medical event or a medically significant event that may not result in death, be immediately life-threatening, or require hospitalization but may be considered serious when, based on appropriate medical judgment, the event may jeopardize the subject or may require medical or surgical intervention to prevent 1 of the outcomes listed above.

#### **8.3.2. Reporting**

Every SAE, regardless of suspected causality (eg, relationship to study drug(s) or study procedure or disease progression), occurring after the subject has signed the ICF through the last study visit (or 30 days after the last dose of study drug, whichever is later) must be reported to the sponsor (or designee) within **24 hours** of learning of its occurrence, unless otherwise specified by the Protocol. Any SAEs occurring more than 30 days after the last dose of study drug should be reported to the sponsor or its designee only if the investigator suspects a causal relationship to the study drug.

Information about all SAEs is collected and recorded on the Adverse Event form of the eCRF. The investigator must assess and record the causal relationship of each SAE to the study treatment.

The investigator must also complete the Incyte Serious Adverse Event Report Form, in English, and send the completed and signed form to the sponsor or designee within 24 hours of becoming aware of the SAE. The investigator must provide a causality assessment, that is, assess whether there is at least a reasonable possibility that the SAE is related to the study treatment: suspected (yes) or not suspected (no). Refer to the Incyte Reference Guide for Completing the Serious Adverse Event Report Form.

The contact information of the sponsor's study-specific representatives is listed in the investigator manual provided to each site. The original copy of the SAE Report Form and the confirmation sheet must be kept at the study site.

Investigational site personnel must report any new information regarding the SAE within 24 hours of becoming aware of the information in the same manner that the initial SAE Report Form was sent. Follow-up information is recorded on an amended or new SAE Report Form, with an indication that it is follow-up to the previously reported SAE and the date of the original report. The follow-up report should include information that was not provided on the previous SAE Report Form, such as the outcome of the event (eg, resolved or ongoing), treatment provided, action taken with study drug because of the SAE (eg, dose reduced, interrupted, or discontinued), or subject disposition (eg, continued or withdrew from study participation). Each recurrence, complication, or progression of the original event should be reported as follow-up to that event, regardless of when it occurs.

If the SAE is not documented in the IB for the study drug (new occurrence) and is thought to be related to the sponsor's study drug, the sponsor or its designee may urgently require further information from the investigator for reporting to health authorities. The sponsor or its designee may need to issue an Investigator Notification (IN) to inform all investigators involved in any study with the same drug that this SAE has been reported. Suspected Unexpected Serious Adverse Reactions (SUSARs) will be collected and reported to the competent authorities and relevant ethics committees in accordance with Directive 2001/20/EC, or as per national regulatory requirements in participating countries.

#### **8.4. Emergency Unblinding of Treatment Assignment**

The procedure for emergency unblinding is provided in the study reference manual. This option may be used ONLY if the subject's well-being requires the investigator to be aware of the subject's treatment assignment.

The investigator should make every effort to contact the sponsor's (or its designee's) clinical research physician or medical monitor before unblinding a subject's treatment assignment; however, this is not mandatory. If a subject's treatment assignment is unblinded, the sponsor or its designee must be notified immediately by telephone.

If an investigator, site personnel performing assessments, or subject is unblinded, the subject must be withdrawn from the study treatment. In cases where there are ethical reasons to have the subject remain in the study, the investigator must obtain specific approval from the sponsor's (or

its designee's) clinical research physician or medical monitor for the subject to continue in the study.

## 8.5. Pregnancy

Pregnancy, in and of itself, is not regarded as an AE unless there is suspicion that study drug may have interfered with the effectiveness of a contraceptive medication or method. When a pregnancy has been confirmed in a subject during maternal or paternal exposure to study drug, the following procedures should be followed in order to ensure subject safety:

- The study drug must be discontinued immediately (female subjects only; see Section 5.5.1 for the maximum permitted duration of study drug interruption).
- The investigator must complete and submit the Incyte Clinical Trial Pregnancy form to the sponsor or its designee within **24 hours** of learning of the pregnancy.

Data on fetal outcome and breastfeeding are collected for regulatory reporting and drug safety evaluation. Follow-up should be conducted for each pregnancy to determine outcome, including spontaneous or voluntary termination, details of the birth, and the presence or absence of any birth defects, congenital abnormalities, or maternal and/or newborn complications, by following until the first well-baby visit. Pregnancy should be recorded on a Clinical Trial Pregnancy form and reported by the investigator to the sponsor or its designee. Pregnancy follow-up information should be recorded on the same form and should include an assessment of the possible causal relationship to the sponsor's study drug to any pregnancy outcome, as well as follow-up to the first well-baby visit or the duration specified in local regulations, whichever is later. Refer to the Incyte Reference Guide for Completing the Clinical Trial Pregnancy Form.

**Any SAE occurring during pregnancy must be recorded on the SAE report form and submitted to the sponsor or designee.**

## 8.6. Warnings and Precautions

Special warnings or precautions for the study drug, derived from safety information collected by the sponsor or its designee, are presented in the Investigator's Brochure (IB). Additional safety information collected between IB updates will be communicated in the form of Investigator Notifications (INs). Any important new safety information should be discussed with the subject during the study, as necessary. If new significant risks are identified, they will be added to the ICF.

## 8.7. Data Monitoring Committee

An independent DMC will be formed. The DMC will consist of qualified individuals who are not involved with the conduct of the study. The establishment, composition, roles, duties, and responsibilities of the DMC are addressed in the approved DMC charter.

## 8.8. Adverse Events of Special Interest

All reported AEs will be collected. [REDACTED]

## 8.9. Product Complaints

The sponsor collects product complaints on study drugs and drug delivery systems used in clinical studies in order to ensure the safety of study participants, monitor quality, and facilitate process and product improvements.

All product complaints associated with material packaged, labeled, and released by the sponsor or its designee will be reported to the sponsor. All product complaints associated with other study material will be reported directly to the respective manufacturer.

The investigator or his/her designee is responsible for reporting a complete description of the product complaint via email or other written communication to the sponsor contact or respective manufacturer as noted in the packaging information. Any AE associated with a product complaint should be reported as described in Section 8.1.2 of this Protocol.

If the investigator is asked to return the product for investigation, he/she will return a copy of the product complaint communication with the product.

## 9. STATISTICS

### 9.1. Study Populations

The intent-to-treat (ITT) population will include subjects randomized in the study. Treatment groups for this population will be defined according to the treatment assignment at randomization.

The per protocol population will include those ITT subjects who are considered to be sufficiently compliant with the Protocol. The criteria will be detailed in the SAP, and this population is defined for use in supportive sensitivity analyses for the primary efficacy endpoint.

The safety evaluable population will include randomized subjects who received at least 1 dose of study drug.

### 9.2. Selection of Sample Size

Based on a literature search and the Incyte Phase 2 study (INCB 18424-256) and a difference in response rate of 25% (30% vs 5%), a total of approximately 120 subjects (60 subjects per group) would provide approximately 90% power to detect a treatment difference of 25% in the primary endpoint at 2-sided chi-square test with an alpha level of 0.05.

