**Statistical Methods:**

When the last subject reaches Week 52 or discontinues, the database will be cleaned, locked and the final analyses will be conducted.

Selection of Sample Size

Based on a literature search and the Incyte Phase 2 study (INCB 18424-256) and a difference in response rate of 25% (30% vs 5%), a total of approximately 120 subjects (60 subjects per group) would provide approximately 90% power to detect a treatment difference of 25% in the primary endpoint at 2-sided chi-square test with an alpha level of 0.05.

Primary Efficacy Analysis

The primary efficacy endpoint is the proportion of subjects who achieve a simultaneous reduction of platelet counts to  $< 600 \times 10^9/L$  with a reduction of WBCs to  $< 10 \times 10^9/L$  for at least 80% of biweekly assessments for 12 consecutive weeks between Weeks 32 and Week 52. The proportion of subjects who meet the response criteria will be estimated with a 95% confidence interval. The Cochran-Mantel-Haenszel test stratified by JAK2V617F mutation status, screening platelet count, and prior anagrelide use will be applied to compare the 2 treatment groups. The test will be 2-sided at 5% significant level. The overall stratum-adjusted odds ratio, along with its 95% confidence interval, will be presented.

In the analysis of the primary efficacy endpoint, subjects who discontinue study treatment without meeting the response criteria will be considered as nonresponders. Subjects who meet the primary endpoint criteria of a response but discontinue treatment before Week 52 will be considered as responders.

Secondary Efficacy Analyses

- Proportion of subjects who achieve CR or PR at Week 32, as defined by ELN 2013 response criteria. The analysis will be conducted in the same fashion as the primary analysis.
- Duration of responses for subjects who achieve primary response as defined in the primary efficacy endpoint will be estimated using the Kaplan-Meier method. The start of a response will be the first visit where both platelet control (defined as a reduction to  $< 600 \times 10^9/L$ ) and WBC control (defined as a reduction to  $< 10 \times 10^9/L$ ) are achieved. Loss of response will be defined as 2 consecutive visits where either platelet count is  $\geq 600 \times 10^9/L$  or WBC is  $\geq 10 \times 10^9/L$ . The earlier of the 2 consecutive visits will be used as the end of response time.

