### **3.3. Sample Size Considerations**

Based on a literature search, the Incyte Phase 2 study (INCB 18424-256), and a difference in response rate of 25% (30% vs 5%), a total of approximately 120 subjects (60 subjects per group) would provide about 90% power to detect a treatment difference of 25% in the primary endpoint at 2-sided chi-square test with an alpha level of 0.05.

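### The stated power of about 90% does not follow from the plan's own inputs: 60 per group at 30% versus 5% gives about 96%, and 90% needs about 47 per group

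*Protocol*

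**What the plan says.** Protocol Section 9.2 gives all the inputs for a power calculation: response rates of 30% and 5%, 60 subjects per group, and a "2-sided chi-square test with an alpha level of 0.05". It concludes that this size "would provide approximately 90% power to detect a treatment difference of 25% in the primary endpoint at 2-sided chi-square test with an alpha level". The Synopsis (Statistical Methods) repeats the statement. SAP Section 3.3 uses the same inputs and says the size "would provide about 90% power to detect a treatment difference of 25% in the primary endpoint".

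None of the three places mentions a dropout allowance, a continuity correction, an exact test or a more cautious pair of rates. Allocation is 1:1 (Protocol 4.3). No interim efficacy analysis is planned (Protocol 9.6, SAP 10). The key secondary endpoint is tested only after the primary hypothesis is rejected (Protocol 9.3, SAP 3.2), so the primary test has the full 0.05.

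**The concern.** A sample size statement should be reproducible from the figures it gives, and this one is not. A difference of 25 points from a control rate of 5% is large, and 60 per group is more than it needs for 90% power.

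This is the plan's only numerical justification for the trial's size. Recruitment was a documented difficulty. Protocol Section 1.4.2.2 says the ban on prior anagrelide severely restricted who could enter, and the rationale for Amendment 2 in Appendix K says the same of the platelet and WBC thresholds, which remain. A reader who trusts 90% at 120 subjects would conclude that any shortfall takes the trial below 90%. On the stated inputs that is not so. If an unstated allowance lies behind the 120, part of that cushion is already spent. The text does not let the sponsor tell which is the case.

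**Working it through.** **Inputs** (Protocol 9.2, SAP 3.3): p1 = 0.30, p2 = 0.05, n = 60 per group, two-sided alpha 0.05 (z = 1.960).

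**Attempt to reproduce 90%.** Chi-square test, pooled variance under the null:

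- Mean rate: (0.30 + 0.05)/2 = 0.175.
- SE under the null: √(2 × 0.175 × 0.825 / 60) = 0.06937.
- SE under the alternative: √((0.30 × 0.70 + 0.05 × 0.95) / 60) = 0.06551.
- Power = Φ[(0.25 − 1.960 × 0.06937) / 0.06551] = Φ(1.741) = **95.9%**.

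The stated figure is not reproduced. Other readings at 60 per group:

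| Test | Power |
|---|---|
| Pooled chi-square, formula | 95.9% |
| Unpooled variance, formula | 96.8% |
| Formula with continuity correction (subtract 1/n from the difference) | 93.1% |
| Exact enumeration, Pearson | 97.1% |
| Exact enumeration, continuity-corrected | 95.2% |
| Exact enumeration, Fisher | 95.2% |

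A one-sided 0.05 test gives 98.1%. Reading 60 as the total (30 per group) gives 73.3%. No variant gives 90%.

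**The planned primary test.** The primary analysis is a CMH test over three binary factors, eight strata (Protocol 9.4.1.1, SAP 7.2.1). The documents give no stratum shares, so these had to be assumed. With 55% JAK2V617F positive, 35% with platelets at or above 1000 × 10⁹/L, 30% with prior anagrelide, and 30% versus 5% in every stratum, 20,000 simulated trials gave 97.3% without and 95.1% with continuity correction. Three other assumed mixes gave 96.8% to 97.4%. Stratification does not explain the gap.

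**Size needed for 90%** (z for power = 1.2816):

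- n = [1.960 × √(2 × 0.175 × 0.825) + 1.2816 × √(0.21 + 0.0475)]² / 0.25²
- = (1.0532 + 0.6503)² / 0.0625 = 46.4, so **47 per group**, 94 in total, which is 26 fewer than 120.
- Check: 47 per group gives 90.4% and 46 gives 89.7%.
- With continuity correction the need is 55 per group.

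**Other reference points** (pooled formula): 50 per group gives 92.0%. At 60 per group, 26% versus 5%, a 21-point difference, gives just under 90% (0.8985).

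**Could an unstated allowance explain 120?** Both routes below assume a 20% loss, a figure that is not in the documents.

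- Lost subjects leave the analysis: 47/(1 − 0.20) = 58.75, so 59 per group. The 48 who remain of 60 give 91.0%.
- Losses count as nonresponse and lower both rates by a fifth, to 24% versus 4%: 60 per group gives 89.4%.

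**The case against.** The strongest reply is that 120 contains an ordinary allowance that was not written down. A 20% loss, handled in either of the ways shown above, brings the figure close to 90%. So does a continuity-corrected size of 55 per group with roughly 8% to 10% loss. Attrition was a reasonable worry: Protocol Section 1.2.3.3 reports that 48.7% of ET subjects withdrew from Study INCB 18424-256, although over long follow-up.

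It would also be wrong to say that counting discontinuers as nonresponders removes the issue by itself. That rule keeps the denominator at 60 but lowers the observed rates, unless 30% and 5% already include dropouts. SAP 7.2.1 also counts missing visits as not controlled, which pulls the same way.

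An unstated allowance is thus a plausible origin for the number, but it does not rescue the text. The plan attaches the 25-point difference to the primary endpoint, which is analyzed in all randomized subjects with discontinuers who have not met the criteria counted as nonresponders. On that reading 30% and 5% are the rates to be analyzed, and no further loss applies. On any other reading an assumption is missing.

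It is also fair to say that the discrepancy is conservative and that the surplus depends on the assumed rates. At 60 per group, 25% versus 5% gives 87.6% and 30% versus 8% gives 87.7%. The higher power is therefore not a licence to stop early.

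**Conclusion.** The point holds. With 30% versus 5%, 60 per group and a two-sided test at 0.05, power is about 96% (95.9% by formula, 97.1% by exact Pearson, 93% to 95% with continuity correction or Fisher). The type II error is 4.1% by formula or 2.9% exactly, against the 10% stated. A power of 90% corresponds to 47 per group (55 with continuity correction) or, at 60 per group, to about 26% versus 5%.

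This rests on the stated rates being those of the primary endpoint as analyzed. The consequence is limited. The trial is not underpowered at its stated effect, and the primary test, the analysis population and the enrollment target are unaffected. It is still an error in the sample size justification, repeated in three places, and should be corrected.

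**What to change.** In the Synopsis, Protocol Section 9.2 and SAP Section 3.3, state that 60 subjects per group give about 96% power for 30% versus 5% with the two-sided chi-square test at 0.05. Add for reference that 90% power corresponds to about 47 per group, or to about 26% versus 5% at 60 per group. Say whether the 30% and 5% already count discontinuers and missing visits as nonresponse.

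If 120 was chosen with a dropout allowance, a continuity correction or lower expected rates, state that assumption and the calculation that leads to 90%.

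The cost is wording in three places, with no change to enrollment or analysis.
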